## 2. STUDY OBJECTIVE AND DESIGN

### 2.1 STUDY OBJECTIVE

Assess improvement in overall lifting of submental (under the chin) and neck tissue as determined by a quantitative measure of tissue lift in the area using photographs taken with Mirror Photofile software and a Vectra 3D digital imaging system in each of the treatment groups in Chinese subjects.

### 2.2 STUDY DESIGN

This study is an open-label, non-randomized clinical study to be conducted at up to seven clinical sites. Approximately 60 subjects (20 subjects per treatment group) who meet the eligibility criteria will be enrolled and treated with the Ulthera® System. Enrollment eligibility will be determined by the physician and trained assessors' review and approval of screening images.

Eligible subjects enrolled in the study will be treated using the Ulthera® System by the study investigator and/or trained clinician. Standardized images will be taken at screening, baseline (prior to treatment) and following treatment (30 to 60 minutes post-treatment) and at the 90-day post treatment visit using Mirror Photofile software and a Vectra 3D digital imaging system.

### 2.3 DURATION OF STUDY

Following the treatment visit, subjects will be followed for a total duration of up to 104 days.

CONFIDENTIAL – PROPRIETARY INFORMATION

### 3. STUDY PROCEDURES

#### 3.1 SCHEDULE OF ASSESSMENTS AT EACH STUDY VISIT

**Table 3.1-1** provides an overview of the subject screening procedure, baseline evaluation, treatment plan, and follow-up requirements.

**TABLE 3.1-1 SCHEDULE OF ASSESSMENTS**

Evaluation / Procedure	Screening Visit	Baseline / Treatment Visit	Day 7 ± 3 Follow-up	Day 90 ± 14 Follow-up
Informed Consent	√			
Eligibility Assessment (Inclusion/Exclusion  )	√			
Demographics, Medical History, BMI	√			√ 
Pregnancy Screening	√ 			√
Investigator Skin Examination 	√	√		
Selection/Documentation of Treatment Plan 		√		
Treatment of Lower Face, Submental, and Neck		√		
Subject Assessment of Pain 		√		
Vectra 3D Images		√ 		√ 
Quantitative Submental Lift Measure 		√		√
Masked Qualitative Assessments 		√		√
Patient Satisfaction Questionnaire				√
Aesthetic Improvement (Physician Global Aesthetics Improvement Scale - PGAIS)				√
Aesthetic Improvement (Subject Global Aesthetics Improvement Scale - SGAIS)				√
Adverse Event Assessment		*	*	*

\*Complete AE Form when necessary.

1. Screening Form
2. Baseline Clinical Observations (Pre-Treatment) or Clinical Safety and Adverse Events (Post-Treatment and at Follow-up Intervals).
3. Treatment Parameters System Record
4. Subject Pain Assessment Scale using a validated Numeric Rating Scale. Pain scores should be obtained following each region treated and for each transducer used. Record the average pain score for the entire region treated. Overall pain assessment will be completed following treatment completion.
5. Post-treatment images taken 30-60 minutes following Ultherapy® treatment.
6. Pregnancy:
  - a. If a subject becomes pregnant after the Baseline visit and study treatment has been completed, the subject should continue to be followed.
  - b. If a subject becomes pregnant after the Baseline visit but before any study treatments, the subject should be exited from the study.
7. Baseline and 90 day photos to be used after study completion to complete assessment.
8. Obtain height and weight for BMI
9. Subjects may be asked to return to retake Day 90 image if photography issues are noticed following image assessment by photography consultant.

CONFIDENTIAL – PROPRIETARY INFORMATION

## 4. SUBJECT SELECTION AND PRE-TREATMENT

The study population will consist of healthy Chinese (both parents of full Chinese descent) males and females between 35 to 65 years of age with mild to moderate submental (under the chin) and neck tissue laxity and adequate menton area to allow for quantitative analysis, who have chosen to participate in this clinical study as evidenced by execution of the informed consent document. A physician assessor will confirm subjects eligibility based on submental (under the chin) and neck tissue laxity. Screening photos will be provided in a blinded manner so the trained assessor has no knowledge of what site is considering enrolling the patient.

### 4.1 PRE-TREATMENT RECRUITING/SCREENING

Subjects will be recruited from the study site's patient database and IRB approved advertisements. Study site personnel will explain the design and purpose of the study to potential study subjects. Subjects interested in participating will visit the study site where informed consent will be obtained.

### 4.2 INFORMED CONSENT

Written informed consent will be obtained from all subjects (or legal representatives) before any study-related procedures, including any pre-treatment screening procedures, are performed. Investigators or delegated study personnel may discuss the availability of the study and the possibility for entry with a potential subject without first obtaining consent. Informed consent must be obtained and documented prior to initiation of any procedures that are performed solely for the purpose of determining eligibility for research.

Investigators have ethical and legal responsibilities to ensure that the protocol is clearly explained to each subject considered for enrollment in the study. Compliance with this requirement should be documented on a written Informed Consent Form approved by the reviewing IRB.

The IRB-approved Informed Consent Form will be signed by the study personnel obtaining consent. The subject will be given a copy of the signed Informed Consent Form. The investigative site will keep the original on file.

### 4.3 ELIGIBILITY

#### 4.3.1 INCLUSION CRITERIA

Subjects must meet all of the following criteria for study enrollment:

1. Male or female, age 35 to 65 years.
2. Both parents of full Chinese descent.
3. Mild to moderate skin laxity of the submental (under the chin) and neck tissue as determined by physician and trained assessors.
4. Adequate menton area to allow for quantitative analysis, as confirmed by photography images.
5. Willingness and ability to comply with protocol requirements, including returning for follow-up visit and abstaining from any other procedures in the areas to be treated through the follow-up period.
6. Subjects of childbearing potential must have a negative urine pregnancy test result and must not be lactating at the Screening Visit and be willing and able to use an acceptable method of birth control (e.g. barrier methods used with a spermicidal agent, hormonal methods, IUD, surgical sterilization, abstinence) during the study. Women will not be considered of childbearing potential if one of the following conditions is documented on the medical history:
  - a. Postmenopausal with last menstrual bleeding at least 12 months prior to study; and

CONFIDENTIAL – PROPRIETARY INFORMATION

- b. Without a uterus and/or both ovaries.
7. Willing to take 600mg Ibuprofen as pre-treatment medication at least 60 minutes but not more than two hours prior to study treatment.
8. Willingness and ability to provide written consent for study-required photography and adherence to photography procedures (i.e., removal of jewelry and makeup).
9. Willingness and ability to provide IRB approved written informed consent prior to performance of any study-related procedure.

#### 4.3.2 EXCLUSION CRITERIA

Subjects will be excluded if they meet any of the following criteria:

1. Presence of an active systemic or local skin disease that may affect wound healing.
2. Presence of any hemorrhagic disorder or hemostatic dysfunction, herpes simplex, diabetes, epilepsy, bell's palsy or any physical or psychological condition that is deemed unacceptable by the investigator for participation in this study.
3. Severe solar elastosis.
4. Excessive subcutaneous fat in the area(s) to be treated.
5. Excessive skin laxity on the area(s) to be treated.
6. Significant scarring in the area(s) to be treated that would interfere with assessing results.
7. Open wounds or lesions in the area(s) to be treated.
8. Severe or cystic acne on the area(s) to be treated.
9. Active implants (e.g., pacemakers or defibrillators), or metallic implants in the treatment areas (dental implants not included.)
10. Inability to understand the protocol or to give informed consent.
11. Allergy or sensitivity to pre-treatment medication (ibuprofen).
12. Microdermabrasion, or prescription level glycolic acid treatment to the treatment area(s) within four weeks prior to study participation or during the study.
13. Marked asymmetry, ptosis, excessive dermatochalasis, deep dermal scarring, or thick sebaceous skin in the area(s) to be treated.
14. BMI greater than or equal to 30.
15. History of chronic drug or alcohol abuse.
16. More than 2-3 does of any NSAID in any 2-week period prior to and throughout study.
17. History of autoimmune disease.
18. Concurrent therapy that, in the investigator's opinion, would interfere with the evaluation of the safety or efficacy of the study device.
19. Subjects who anticipate the need for inpatient surgery or overnight hospitalization during the study.
20. Subjects who, in the investigator's opinion, have a history of poor cooperation, noncompliance with medical treatment, or unreliability.
21. Concurrent enrollment or enrollment in any study involving the use of investigational devices or drugs within the past three months.
22. Current smoker as defined by:
  - a. Having smoked one or more cigarettes per day on a daily basis within the past year; or
  - b. Smoke cessation within the past 6 months.
23. Current user of any nicotine-containing products, e.g., e-cigarettes, Nicorette gum, nicotine patches, etc.
24. History of the following cosmetic treatments in the area(s) to be treated:
  - a. Skin tightening procedure within the past year;

CONFIDENTIAL – PROPRIETARY INFORMATION

- b. Injectable filler of any type within the past:
    - i. 9 months for Hyaluronic acid fillers (e.g. Restylane)
    - ii. 24 months for Ca Hydroxyapatite fillers (e.g. Radiesse)
    - iii. 12 months for Long-lasting Hyaluronic acid (Juvéderm Voluma)
    - iv. 24 months for Poly-L-Lactic acid fillers (e.g. Sculptra); and
    - v. Ever for permanent fillers (e.g. Silicone, Artecoll)
  - c. Neurotoxins within the past three months;
  - d. Ablative resurfacing laser treatment;
  - e. Nonablative, rejuvenative laser or light treatment within the past six months;
  - f. Surgical dermabrasion or deep facial peels;
  - g. Facelifts within the past year; or
  - h. Any history of contour threads.
25. History (in the prior year) or current use of the following prescription medications:
- a. Accutane or other systemic retinoids within the past six months;
  - b. Topical Retinoids within the past two weeks;
  - c. Antiplatelet agents/Anticoagulants (Coumadin, Heparin, Plavix);
  - d. Psychiatric drugs that in the investigators opinion would impair the subject from understanding the protocol requirements or understanding and signing the informed consent.

After subjects have provided informed consent and met the inclusion/exclusion criteria, the study procedures described in the following section will be performed.

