Inclusion Criteria:	
 
1. Male or female, age 35 to 65 years.
 
2. Both parents of full Chinese decent.
 
3. Mild to moderate skin laxity of the submental (under the chin) and neck tissue as determined by the physician and trained assessors.
 
4. Adequate menton area to allow for quantitative analysis, as confirmed by photography images.
 
5. Willingness and ability to comply with protocol requirements, including returning for follow-up visit and abstaining from any other procedures in the areas to be treated through the follow-up period.
 
6. Subjects of childbearing potential must have a negative urine pregnancy test result and must not be lactating at the Screening Visit and be willing and able to use an acceptable method of birth control (e.g. barrier methods used with a spermicidal agent, hormonal methods, IUD, surgical sterilization, abstinence) during the study. Women will not be considered of childbearing potential if one of the following conditions is documented on the medical history: 
 
a. Postmenopausal with last menstrual bleeding at least 12 months prior to study; and
 
b. Without a uterus and/or both ovaries.
 
 
 
7. Willing to take 600mg Ibuprofen as pre-treatment medication, at least 60 minutes but not more than two hours prior to study treatment.
 
8. Willingness and ability to provide written consent for study-required photography and adherence to photography procedures (i.e., removal of jewelry and makeup).
 
9. Willingness and ability to provide written informed consent prior to performance of any study-related procedure.
 

Exclusion Criteria:	
 
1. Presence of an active systemic or local skin disease that may affect wound healing.
 
2. Presence of any hemorrhagic disorder or hemostatic dysfunction, herpes simplex, diabetes, epilepsy, bell’s palsy or any physical or psychological condition that is deemed unacceptable by the investigator for participation in this study.
 
3. Severe solar elastosis.
 

CONFIDENTIAL – PROPRIETARY INFORMATION

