#### 5.1.2 PRE-TREATMENT MEDICATIONS

[figure not shown]
For this protocol, pre-treatment medication will be administered on-site and restricted to Ibuprofen (600mg) taken at least 60 minutes but not more than two hours prior to study treatment.

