**TABLE 8.1.1 EXPECTED TREATMENT EFFECTS**

Expected Treatment Effects	Duration
Bruising/Ecchymosis	Up to 3 weeks
Edema/Swelling	Up to 2 weeks
Erythema/Redness	Up to 24 hours
Local Muscle Weakness/Paresis	Up to 6 weeks
Nodules	Up to 4 weeks
Acute Pain	Immediate/momentary (while energy is being delivered) - 2 hours
Skin Burn	Up to 4 weeks
Tenderness/Soreness/Pain/Sensitivity to Touch	Up to 6 weeks
Tingling/Paresthesia/Numbness	Up to 6 weeks
Welting/Raised Areas of Edema	Up to 4 week

Common risks associated with Ibuprofen include nausea, diarrhea, dizziness, headaches and hypertension. NSAIDs (e.g., Ibuprofen) should not be given to patients who have experienced asthma, urticaria, or allergic-type reactions after taking aspirin or other NSAIDs.

These risks will be minimized or reduced by monitoring the subject during the treatment and observing the skin's response to receiving the treatment. If the treatment is not tolerated, the investigator must stop administering treatment for the subject's safety, and the subject will be followed for adverse events for 90 days.

Previous clinical studies with the Ulthera® System have shown that the sensory response was tolerable from the subject's and investigator's perspectives. The discomfort was transient and no subject had any residual pain beyond 30 minutes.

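### Exclusion 11 covers reactions to ibuprofen only, while Section 8.1 of the protocol also rules out NSAIDs after reactions to aspirin or other NSAIDs

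*Protocol*

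**What the plan says.** Ibuprofen is built into the treatment visit for every subject. Inclusion 7 in Section 4.3.1 requires the candidate to be "Willing to take 600mg Ibuprofen as pre-treatment medication at least 60 minutes but not more than two hours prior to study treatment", and the synopsis has the same criterion. Section 5.1.2 adds that "pre-treatment medication will be administered on-site and restricted to Ibuprofen (600mg"; no alternative is named.

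The exclusion that guards against a reaction to this drug is no. 11, worded identically in the synopsis and in Section 4.3.2: "Allergy or sensitivity to pre-treatment medication (ibuprofen".

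The text under Table 8.1.1 in Section 8.1 describes who should not receive the drug: "NSAIDs (e.g., Ibuprofen) should not be given to patients who have experienced asthma, urticaria, or allergic-type reactions after taking aspirin or other NSAIDs".

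Two other exclusions bear on the point. No. 16 reads "More than 2-3 does of any NSAID in any 2-week period prior to and throughout study". No. 2 includes a general clause for "any physical or psychological condition that is deemed unacceptable by the investigator for participation in this study".

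**The concern.** The eligibility list and the protocol's own risk statement describe different groups of people for a drug that all subjects are asked to take. The risk statement is the wider of the two. Sites screen against the numbered list, so a contraindication found only in a paragraph below a table of device effects can be missed. What is at stake is subject safety: someone with, for example, a history of asthma after aspirin could be enrolled and scheduled for an NSAID that the protocol says they should not have. Endpoints, sample size and analysis are not at issue.

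**Working it through.** There is no figure in the plan to reproduce. The check compares the texts and then traces a candidate through them.

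**1. The two groups side by side**

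| | Exclusion 11 | Section 8.1 |
|---|---|---|
| Drug that caused the reaction | Ibuprofen | Aspirin or other NSAIDs |
| Type of reaction | Allergy or sensitivity | Asthma, urticaria, allergic-type reaction |
| Status | Mandatory exclusion | Statement in the risk section |

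The people covered by Section 8.1 but not by the wording of exclusion 11 are those who reacted to aspirin or to an NSAID other than ibuprofen and have no known reaction to ibuprofen.

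**2. Does another criterion cover them?** Sections 4.3.1 and 4.3.2 contain 9 + 25 = 34 numbered criteria.

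- Criteria that mention ibuprofen: 2 (inclusion 7, which asks for willingness, and exclusion 11).
- Criteria that mention NSAIDs as a class: 1 (exclusion 16). It limits the number of doses. A person who avoids NSAIDs after a reaction passes it easily.
- Exclusion 25c concerns use of antiplatelet agents or anticoagulants, not reactions to them.
- Exclusion 2 allows the investigator to exclude such a person but does not require it, and it mentions neither aspirin nor NSAIDs.
- Criteria that name a past reaction to aspirin or to another NSAID: 0.

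**3. Tracing a candidate.** Take a person with urticaria after aspirin who has never knowingly reacted to ibuprofen.

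- Inclusion 7 is met if they are willing to take the drug.
- Exclusion 11, as worded, does not apply.
- Exclusion 16 does not apply.
- The person is therefore eligible on the listed criteria. At the treatment visit ibuprofen is due between 60 and 120 minutes before treatment. It is withheld only if the person declines, the investigator uses exclusion 2, or the investigator recalls and applies Section 8.1.

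**4. If the case is caught only at the treatment visit.** Section 5.1.2 offers no substitute, so treating without ibuprofen departs from that section and yields pain scores collected under different conditions from everyone else's. If the person is not treated, they do not fit the definition of a screen failure in Section 4.4, because they did not fail an eligibility criterion. Section 5.7 then counts them as enrolled, and Section 5.6 says withdrawn subjects are not replaced. Settling the matter at screening avoids all of this.

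**The case against.** The strongest reply is that the protocol already contains the prohibition. Section 8.1 names ibuprofen, the patients and the instruction, and investigators are bound by the whole protocol. On this view nothing conflicts, and the only question is where the rule is written. In addition:

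- An investigator who reads exclusion 11 together with Section 8.1 could reasonably count a reaction to aspirin as sensitivity to ibuprofen.
- Medical history is taken at screening and reviewed again before treatment (Table 3.1-1, Section 5.2).
- Ibuprofen is given on site, so staff control the dose.
- The Screening Form is not among the documents and may already ask the question.

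Most of this is fair, and it limits the size of the problem. It does not remove it. The broader reading of exclusion 11 is possible, but the criterion names only ibuprofen. The history review is general and does not direct anyone to ask about aspirin or NSAIDs. On-site dosing puts staff nearby but does not by itself stop the dose. Each safeguard depends on someone making a connection that the eligibility list could make for them.

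One further point should be given little weight. After the NSAID warning, Section 8.1 says "These risks will be minimized or reduced by monitoring the subject during the treatment". Monitoring during treatment would come too late to prevent a dose taken at least 60 minutes earlier. But that sentence goes on to the skin's response and mainly concerns the device, so it is weak evidence either way. The conclusion does not rest on it.

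**Conclusion.** The concern holds. A candidate with a past reaction to aspirin or to another NSAID, and none known to ibuprofen, can pass all 34 listed criteria and arrive at a visit where ibuprofen is the only permitted pre-medication. It should be fixed, because it concerns safety and the remedy is simple, but it is not a case of the protocol telling sites to give the drug: Section 8.1 tells them not to.

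Up to 60 subjects are to be treated and so asked to take ibuprofen. That is the number exposed, not the number at risk. The documents give no frequency for this history among candidates, and none is assumed here. The conclusion rests on exclusion 11 being read as worded and on the Screening Form, which was not available, not already asking the question.

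**What to change.** Reword exclusion 11, in both the synopsis and Section 4.3.2, along these lines: *Allergy or sensitivity to ibuprofen, or a history of asthma, urticaria or allergic-type reaction to aspirin or any other NSAID.* Then confirm that the Screening Form asks the same question.

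The cost is one line in two places of the protocol, and possibly a few more screen failures, all among people whom Section 8.1 already says should not receive the drug.

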#### 4.4 SCREEN FAILURES

A screen failure subject is one from whom informed consent is obtained and is documented in writing (i.e., subject signs an Informed Consent Form), but who does not receive a study treatment because of failure to meet all of the eligibility criteria.

#### 4.5 SUBJECT TREATMENT GROUP ASSIGNMENT

Subjects are not randomized in this study. All subjects will receive an Ultherapy™ treatment at dual depth using the 4-4.5mm and 7-3.0mm transducers. Treatments will be provided to the lower face, submental (under the chin) and neck area. See Section 5.1 for Study Treatment details. Enrolled subjects will be assigned to one of 3 treatment groups:

Group EL2: Subjects will receive an Ultherapy™ treatment at energy level 2 (EL2).

Group EL3: Subjects will receive an Ultherapy™ treatment at energy level 3 (EL3).

Group EL4: Subjects will receive an Ultherapy™ treatment at energy level 4 (EL4).

Twenty subjects will be enrolled in each group. Enrollment from the original protocol was in the following order: EL3, EL4 and EL2. This amendment (dated 26JAN2018) is to change the order of enrollment. Following amendment approval, approximately 20 patients will be enrolled in EL2, EL3 and EL4 respectively. Enrollment will continue at an energy level until that treatment group is complete.

CONFIDENTIAL – PROPRIETARY INFORMATION

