Statistical Analysis:	
Descriptive statistics will be used to compare the submental lift, secondary endpoints and safety assessments between the 3 treatment groups at day 90 in this observational trial.

Study Hypothesis:	
The hypothesis for this study is improvement in overall lifting and tightening of skin from baseline to 90 days post-treatment. For each treatment group (energy level), the measure of pre and Day 90 post treatment area of the chin and neck will determine the amount of tissue lift.

Study Duration:	
Estimated timeline: Up to 12 months

CONFIDENTIAL – PROPRIETARY INFORMATION

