### 5.3.1 PRIMARY ENDPOINT

The primary endpoint is an assessment of the mean change (improvement) in overall lifting and tightening of skin in Chinese subjects at 90-days compared to baseline in each of the treatment groups as determined by a modified version of the validated quantitative measure of tissue lift in neck/submentum using photographs taken with Mirror Photofile software and a Vectra 3D digital imaging system.

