## 6.1 EFFICACY ANALYSIS

The primary analysis of efficacy will be based on the evaluable treated subjects, hence, only those subjects who received a complete or partial study treatment and completed the follow-up visit, and who have evaluable images

CONFIDENTIAL – PROPRIETARY INFORMATION

at baseline and 90-days post-treatment will be included in the analysis. No imputations will be performed for missing data.

The primary efficacy endpoint is the amount of improvement from baseline at 90 days after treatment. Descriptive statistics will compare mean values of improvement between the 3 treatment groups and 95% confidence intervals (CIs) will be calculated for each group. Additionally, the proportion of subjects achieving various levels of improvement may be calculated along with exact 95% CIs.

Any deviations from this statistical analysis plan will be documented with justification in the final report.

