## 6.2 SECONDARY ANALYSES

The frequency and percentage for each of the following secondary endpoints will be reported for available data for the total population and by treatment group.

1. Improvement in overall lifting and tightening of skin as determined by subject response rate (improved, or much improved) on Physician Global Aesthetic Improvement Scale (PGAIS) as determined by live assessment at 90 days post-treatment compared to baseline photograph.
2. Improvement in overall lifting and tightening of skin as determined by subject response rate (improved, or much improved) on Subject Global Aesthetic Improvement Scale (SGAIS) as determined by live assessment at 90 days post-treatment compared to baseline photograph.
3. Improvement in overall lifting and tightening of skin as determined by a masked, qualitative assessment of photographs at 90 days post-treatment compared to baseline.
4. Subject satisfaction and subject reported improvement at 90 days post-treatment.

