## 6.3 SAFETY ANALYSES

All adverse events (AE) and device related adverse events will be collected and reported during this study. AEs will be summarized overall, by seriousness and device relatedness including count, proportion of subjects experiencing each type of AE for all subjects and by treatment group will be provided.

Patient reported pain assessments collected throughout this study using the validated numeric scale will also be reported by treatment group and time point using descriptive statistics and include mean, standard deviation, median and range at minimum.

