## **1. INTRODUCTION**

This Statistical Analysis Plan (SAP) is based on the study Protocol Amendment 1 Final v4.0 dated January 26, 2018.

This document provides additional details concerning the statistical analyses outlined in the protocol and reflects any changes to the protocol from any amendments. This plan will not repeat all the definitions given in the protocol but will provide further details of the summaries and analyses planned therein.

The analysis described in this document is only a part of the efficacy analysis outlined in the study protocol to assess the improvement in overall lifting and tightening of skin as determined by a masked, qualitative assessment of photographs at 90 days post-treatment compared to baseline. The analyses for all the other endpoints will be included in a separate statistical analysis plan.

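### Energy levels are filled one after another without randomisation: does the planned side-by-side comparison of levels need to change?

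*Protocol*

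**What the plan says.** Protocol Section 4.5 states that subjects are not randomised. The amendment of 26 January 2018 changed the order of enrolment from EL3, EL4, EL2 to EL2, EL3, EL4, and "Enrollment will continue at an energy level until that treatment group is complete".

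Two places speak of comparing the levels. The Synopsis (Statistical Analysis) says: "Descriptive statistics will be used to compare the submental lift, secondary endpoints and safety assessments between the 3 treatment groups at day 90". The same sentence goes on to call the trial observational. Section 6.1 says: "Descriptive statistics will compare mean values of improvement between the 3 treatment groups", and it calculates a 95% confidence interval for each group.

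The other analysis sections summarise by level. Secondary endpoints "will be reported for available data for the total population and by treatment group" (Section 6.2), and adverse event counts and proportions "for all subjects and by treatment group will be provided" (Section 6.3).

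The aims are set within each level. The objective is to assess lift "in each of the treatment groups in Chinese subjects" (Section 2.1), and the primary endpoint is mean change "compared to baseline in each of the treatment groups" (Section 5.3.1).

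The supplied SAP covers only the masked photographic endpoint: "The analyses for all the other endpoints will be included in a separate statistical analysis plan". Its Section 8 tabulates responders by group and overall.

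**The concern.** Each level occupies its own stretch of calendar time. Anything that changes during accrual changes together with energy: operator experience, the kind of patient recruited, possibly the mix among up to seven sites. Neither the protocol's analysis sections nor the supplied SAP adjusts for period or site, or says how a difference between levels should be read. If the three columns are taken as a dose response, a trend over time could pass for an energy effect, or could hide one. Some outcomes are especially open to this. The GAIS ratings are made live in an open-label study, and pain and adverse events are recorded while each level is running.

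Section 4.5 also leaves open whether anyone treated under the earlier order, EL3 first, counts toward the 20 in that level.

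**Working it through.** **Inputs.** 20 subjects per level, 60 in all (Section 2.2); filling in sequence and both enrolment orders (Section 4.5). The documents give no SD, effect size, power or drift, so there is no figure of the plan's own to reproduce. Results are in SD units.

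**Assumptions.** Even accrual; linear drift; *k* earlier EL3 subjects counting toward the 20; EL4 not started before the amendment. The documents give neither *k* nor that last point.

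**Share of drift in each contrast.** The order is EL3 (*k*), EL2 (20), EL3 (20 − *k*), EL4 (20). Mean positions on a 0 to 60 scale are:

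- EL2: *k* + 10
- EL3: 30 − *k*
- EL4: 50

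The shares of the total drift are therefore:

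- EL4 − EL2: (40 − *k*)/60
- EL4 − EL3: (20 + *k*)/60
- EL3 − EL2: (20 − 2*k*)/60

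| *k* | EL4 − EL2 | EL4 − EL3 | EL3 − EL2 |
|---|---|---|---|
| 0 | 0.67 | 0.33 | 0.33 |
| 5 | 0.58 | 0.42 | 0.17 |
| 10 | 0.50 | 0.50 | 0.00 |
| 15 | 0.42 | 0.58 | −0.17 |
| 20 | 0.33 | 0.67 | −0.33 |

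The first two shares sum to 1, so one of them is always at least 0.50. The value of *k* moves the problem between contrasts but does not remove it.

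**Size against sampling error.** The 95% half-width for a difference between two levels is t(57) × √(2/20) = 0.63 SD. An assumed drift of 0.5 SD over accrual biases the worst-hit contrast by 0.5 × 0.50 = 0.25 SD to 0.5 × 0.67 = 0.33 SD, about half of that width. With no drift the bias is 0.

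**Would adjusting for time help?** The unadjusted variance of a contrast is 2/20 = 0.100. With linear time in the model, the variance of EL4 − EL2 is 0.902 at *k* = 0, a factor of 9.0 (half-width 1.90 SD). At *k* = 10 it is 0.250, a factor of 2.5 (half-width 1.00 SD). Over *k* from 0 to 20, the contrast with the largest share never has a factor below 2.5. Adjustment would give an interval too wide to use.

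**Which planned results depend on the contrast?**

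- Primary result: a mean change and 95% interval per level, with half-width t(19)/√20 = 0.47 SD. The order in which levels are filled does not enter.
- Secondary and safety results: frequencies or summaries by level. Setting these side by side is what a descriptive comparison amounts to, so the Synopsis promises no more than Sections 6.2 and 6.3 deliver.
- Masked photographic result: responder percentages by level, each from a subject's own pair of photographs.

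None of these is a test, an interval for a difference or a ranking of levels.

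**Earlier EL3 subjects.** The Synopsis caps treated subjects at 60, with up to 20 per level. Another full 20 at every level on top of earlier subjects would break that cap, so the natural reading is that earlier subjects count. Section 6.1 takes all evaluable treated subjects, and SAP Section 6 takes all enrolled subjects with both photographs, so both populations would include them without a further rule. No text says that anyone was treated before the amendment.

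**The case for a change.** The strongest case for a change is that leaving out a p-value does not leave out confounding. Section 1.4 says the study evaluates safety and efficacy at all three levels, so readers will compare the columns, and two sentences of the protocol invite them to. Reading photographs after study completion (Study Overview, note 7), eligibility review blinded to site (Section 4), standardised photography (Section 4.6), fixed energy settings (Section 5.1.4) and repeat images (Section 5.4) make drift less likely. None of them separates energy from period. A caveat and a table of enrolment dates and sites by level would cost little.

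The confounding stands, and a report that read a gradient across levels as an energy effect would be wrong. The case for amending the plan does not stand. The documents call the study a pilot, open-label, non-randomised and observational, and they make no causal claim about energy. Rewording Section 6.1 to report a mean and interval per group would describe what it already produces. Alignment with site or operator is conjecture, since nothing assigns levels by site or clinician. The separate SAP for the other endpoints was not available, so an adjustment or caveat there cannot be excluded.

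Concurrent random allocation would remove the alignment: in simulation with permuted blocks of 6, the bias was about 0 under the same kind of drift. It would, however, replace the chosen order of enrolment. The documents do not give the reason for that order, and if it is a safety reason the choice is a real trade-off.

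**Conclusion.** The observation is correct, but it is a caveat on interpretation and calls for no change to the plan. Energy level and enrolment period cannot be separated, and at least half of any linear drift would enter one of the contrasts. At an assumed drift of 0.5 SD that is 0.25 to 0.33 SD, within a sampling half-width of 0.63 SD that already rules out a firm reading of differences between levels. The within-level objective, hypothesis and primary endpoint are untouched by this point.

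These sizes rest on even accrual, linear drift, 20 subjects per level and EL4 not having started before the amendment. The size of the drift is assumed, and the documents do not show that any drift exists.

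Analysts would fill what remains as a matter of course. The final report would call differences between levels exploratory, show enrolment dates and sites by level, and state how many subjects, if any, were treated before the amendment. None of this alters a planned result.
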